11.9.6. Two-Month Post-Index Procedure (60 ± 14 Days)

The following data are to be collected:

- Abbreviated physical examination (temperature, systolic/diastolic blood pressure, respiration rate, heart rate)

- Body mass assessment (body weight, calculation of BMI, and measurement of circumferences)
- Concomitant medications

- Assessment of AEs that occurred since the last visit
- Brief lifestyle counseling

11.9.7. Four-Month Post-Index Procedure (120 ± 14 Days)

The following data are to be collected:

- Abbreviated physical examination (temperature, systolic/diastolic blood pressure, respiration rate, heart rate)
- Body mass assessment (body weight, calculation of BMI, and measurement of circumferences)
- Concomitant medications
- Assessment of AEs that occurred since the last visit
- Brief lifestyle counseling

11.9.8. Six-Month Post-Index Procedure (180 ± 14 Days)

The following data are to be collected:

- Abbreviated physical examination (temperature, systolic/diastolic blood pressure, respiration rate, heart rate)
- Body mass assessment (body weight, calculation of BMI, and measurement of circumferences)
- Concomitant medications
- IWQOL-Lite
- Visual Analog Scale assessment
- Eating Inventory assessment
- Blood tests (lipid levels and lipoproteins, glucose, insulin, HbA1c, high sensitivity C-reactive protein)

- Assessment of AEs that occurred since the last visit
- Brief lifestyle counseling

11.9.9. Nine-Month Post-Index Procedure (270 ± 21 Days)

The following data are to be collected:

- Abbreviated physical examination (temperature, systolic/diastolic blood pressure, respiration rate, heart rate)
- Body mass assessment (body weight, calculation of BMI, and measurement of circumferences)
- Concomitant medications
- Assessment of AEs that occurred since the last visit
- Brief lifestyle counseling

11.9.10. Twelve-Month Post-Index Procedure (365 ± 30 Days)

The following data are to be collected:

- Physical examination

- Body mass assessment (body weight, calculation of BMI, and measurement of circumferences)
- Concomitant medications
- IWQOL-Lite
- Visual Analog Scale assessment
- Eating Inventory assessment
- Blood tests (lipid levels and lipoproteins, glucose, insulin, HbA1c, high sensitivity C-reactive protein)
- Endoscopic assessment
- Assessment of AEs that occurred since the last visit
- Assessment of blinding
- Brief lifestyle counseling
- Unblinding and Pivotal study exit

The above data are to be collected prior to unblinding with the exception of the endoscopic assessment, which is to be collected at the time of removal.

Subjects who were assigned to the Control group will not require an endoscopy at this visit since device removal is unnecessary but they should remain blinded until the all other data are collected.

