3.5.2. Anticipated Adverse Events (AEs) Associated with the TPS Placement, Residence, and Removal

Anticipated AEs associated with the TPS placement and removal procedures and TPS residence may include, but are not limited to, the following:

- Abdominal cramps and discomfort from the air used to distend the stomach
- Aspiration of gastric contents, aspiration pneumonia
- Complications related to sedation and anesthesia
- Complications related to upper GI endoscopy and the use of routine endoscopic instruments
- Infection in the throat, esophagus, stomach, or duodenum
- Gastric, esophageal, or pharyngeal trauma, including sore or irritated throat, ulceration, bleeding, or perforation in upper GI tract, and their associated complications

- Injury to the digestive tract by the TPS delivery system or during device removal
- TPS placement in an improper location such as in the esophagus or duodenum, which results in obstruction, bleeding, or perforation
- Esophageal sphincter and/or pyloric sphincter incompetency associated with sphincter dilation during placement, residence or removal of the TPS
- Inability to endoscopically remove part or all of the TPS device, which may result in the need for surgery
- Cardiac or respiratory arrest during endoscopy
- Halitosis
- A feeling of heaviness in the abdomen
- Abdominal or back pain, either steady or cyclic
- Gastric discomfort, feelings of nausea, and vomiting
- Constipation or diarrhea
- Dyspepsia
- Allergic reaction to the device's materials (e.g., silicone, barium sulfate and parylene)
- Excess reduction in oral intake, resulting in dehydration or malnutrition
- Alteration of the absorption rate of medications, particularly to enteric-coated medications
- Influence on medication dosing, leading to the need to adjust dosing and potential associated complications if dosing is not adjusted, such as hypoglycemia, hypotension, etc.
- Influence on digestion of food
- Pharyngeal, esophageal, or gastrointestinal obstruction by the TPS
- Formation of intragastric bezoars
- Gastroesophageal reflux
- Distension of stomach
- Injury or irritation to upper GI tract, resulting in acute or chronic tissue inflammatory response, pain, bleeding, erosion, ulceration, strictures, stenosis, or perforation
- Bacterial or fungal growth on the surfaces of the TPS, resulting in infection
- Biliopancreatic infection or obstruction, cholecystitis, pancreatitis

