7.5. Patient Discontinuation

Once enrolled, each subject will remain in the study until the required follow-up period is complete. However, the subject has the right to withdraw from the study at any time without penalty or loss of benefit. The following events will result in terminating the subject's follow-up:

- Subject voluntary withdrawal
- Subject withdrawn by the Investigator as clinically indicated
- Subject becomes pregnant
- Subject lost to follow-up
- Subject death
- Study is terminated according to Section 5.6 (Early Study Termination)

In the case of subject withdrawal from the study, the TPS must be removed before the subject exits the study.

In case the TPS is removed early as described in Section 10.5, the subject's participation in the study is considered terminated. Any Adverse Events will be followed until resolution or stabilization according to Section 12.1.

In case a subject achieves normal BMI (≤ 22 kg/m²) for two consecutive visits before the 12-month follow up, the subject is considered to have completed the study. Subject will exit the study and the device should be removed in the treatment subjects.

A final endoscopy should be performed whenever possible before the Treatment subject exits the study.

The Sponsor must be notified of the reason for subject discontinuation. The site will document this information on the electronic case report form (eCRF) and make every effort to give a full description of the reason for withdrawal. Investigators must also report this information to the local IRB as defined by their institution's procedure.

Subjects who are terminated early will not be replaced by enrolling additional subjects.

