Before the subject is discharged, s/he is to be provided with a subject information card. This card provides the phone number and name of the person to contact in case s/he needs medical attention related to the therapy. Additionally, the subject can provide this card to an emergency room doctor, allowing them to contact the Primary Investigator and obtain information about the study. A sample of the card is provided in Appendix G.

The subject should be placed on a liquid diet for 3 days, followed by soft food for a week, slowly returning to normal food in 10 days.

The following procedures/assessments will be performed during this visit:

- Abbreviated physical examination including vital signs (temperature, systolic/diastolic blood pressure, respiration rate, heart rate)
- Body mass assessment (body weight, calculation of BMI, and measurement of circumferences)
- Assessment of medications
- Endoscopic assessment
- Confirmation of eligibility
- TPS placement procedure

- Assessment of AEs that occurred during the procedure

Post-Procedure Follow-Up Visits

Post-procedure follow-up visits are summarized in Appendix B. They include:

- Office visits at 1 week, and 1, 2, 4, 6, 9, 12 months
- Endoscopic assessments at 2, 6, and 12 months
- Visual Analog Scale assessment at 1 week and 1, 6, and 12 month(s)
- Eating Inventory assessment at 1 week and 1, 6 and 12 month(s)
- Blood tests at 6 and 12 months
- IWQOL-Lite at 6 and 12 months
- Device removal at 12 months
- AE assessments at each follow-up visit
- Brief lifestyle counseling at each follow-up visit and brief telephone calls at 7, 8, 10, and 11 months.

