11.9.10.1. TPS Device Removal

The TPS is to be removed 365 ± 30 days after the index procedure under general or MAC anesthesia. An endoscopic assessment will be performed in all subjects followed by TPS removal in the Treatment group. The device removal procedure is described in detail in the IFU 

Subjects will be discharged according to the hospital and physician's discharge criteria.

All procedure- and device-related AEs must be followed until resolution or stabilization (the Investigator does not expect any further improvement or worsening of the event). Following study exit, follow-up will be according to clinical practice.

Subjects will be informed that his/her participation in this study is complete. The subject's study exit will be documented.

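### In the visible protocol no AE assessment is scheduled after TPS removal, so new harms that start after discharge depend on spontaneous report

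*Combined protocol and SAP*

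**What the plan says.** **At 12 months.** The list in Section 11.9.10 contains "Assessment of AEs that occurred since the last visit". The section then sets the order of collection: "The above data are to be collected prior to unblinding with the exception of the endoscopic assessment". The endoscopy alone is left for the time of removal.

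**At removal.** Section 11.9.10.1 states: "The TPS is to be removed 365 ± 30 days after the index procedure under general or MAC anesthesia". The visible text of that section has no AE item. The subject is discharged, told that participation is over, and exited. Known procedure- and device-related AEs are to be followed until they resolve or stabilize. Otherwise: "Following study exit, follow-up will be according to clinical practice".

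**End of follow-up elsewhere.** Section 5.1 ends follow-up at 12 months or at device removal. Section 7.5 covers the early case ("In case the TPS is removed early as described in Section 10.5") and treats participation as terminated, with AEs followed to resolution or stabilization. The last column of Appendix B is 12M, which holds AE assessment, device removal and study exit together.

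**At placement.** Section 11.9.3 requires "Assessment of AEs that occurred during the procedure", and Section 11.9.4 adds a visit at 7 ± 2 days with its own AE item.

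**Expected harms.** Section 3.5.2 covers placement, residence and removal. One entry reads "Injury to the digestive tract by the TPS delivery system or during device removal"; others include perforation, bleeding, aspiration pneumonia and sphincter incompetency.

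**The concern.** Removal is mandatory for every Treatment subject and is done under general or monitored anesthesia. The protocol itself names it as a source of harm. Yet the 12-month AE question looks backward and is asked before the procedure, and no later question is scheduled.

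Safety is half of the study objective in Section 4, and Section 15.5.5 promises AE summaries by relationship to device and to procedure. For removal, those summaries would rest on what staff see before discharge and what former subjects choose to report. Prior experience does little to fill the gap: the feasibility study in Section 3.4.3 had 20 removals of the second-generation device, after 3 or 6 months of residence rather than 12.

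Early removals matter as well. Several triggers in Section 10.5 are ulcer findings, bleeding or unresolved pain, and these subjects also leave the study at removal.

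**Working it through.** **Step 1. Count the scheduled AE assessments after each device procedure** (Sections 11.9.3 to 11.9.10.1 and Appendix B, visible text).

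| Procedure | AE item tied to the procedure | Later scheduled AE visits | Number |
|---|---|---|---|
| Placement, Day 0 | Yes | 1 week; 1, 2, 4, 6, 9, 12 months | 7 |
| Endoscopy, 2 months | AE item at that visit | 4, 6, 9, 12 months | 4 |
| Endoscopy, 6 months | AE item at that visit | 9, 12 months | 2 |
| Removal, 12 months or early | None visible | None | 0 |

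The zero for 12-month removal depends on the order of events. The only item held back to the procedure is the endoscopy ("with the exception of the endoscopic assessment, which is to be collected at the time of removal"), so the AE item belongs to the set collected before unblinding. The 12-month visit and the removal share a ± 30-day window but are not tied to one day, so an interval between the AE item and the removal could also be uncovered.

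**Step 2. Reproduce the plan's safety precision.** Inputs from Section 15.4: n = 180 Treatment subjects, event rate p = 0.9%.

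- Chance of at least one event: 1 − (1 − p)^n = 1 − 0.991^180 = 80.4%. The plan states 80%.
- Exact two-sided 95% upper limit for 0/180: 1 − 0.025^(1/180) = 2.03%. The plan states 2.0%.

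Both figures are right, provided every event is ascertained.

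**Step 3. Relax that condition for delayed post-removal events.** Suppose each such event reaches the database with probability c. The documents give no value for c, so a range is shown. The observable rate is c·p. The detection chance is 1 − (1 − 0.009c)^180, and the true rate compatible with 0/180 observed is 2.03%/c.

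| Assumed c | Chance of at least one observed event at a true rate of 0.9% | True rate compatible with 0/180 observed |
|---|---|---|
| 1.00 | 80.4% | 2.0% |
| 0.75 | 70.5% | 2.7% |
| 0.50 | 55.6% | 4.1% |
| 0.25 | 33.3% | 8.1% |

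This applies only to events that start after discharge from removal. Events during placement and residence keep the precision of Section 15.4.

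**The case against.** The strongest reply is that the protocol does not close AE recording at removal, and this stands. Section 12.1 says an adverse device effect may occur at any time after exposure. Section 12.3.2 has the Investigator record all AEs and device effects. Sections 7.5 and 11.9.10.1 require follow-up to resolution or stabilization, which presupposes that removal events are written down. No AE cut-off date is stated, and the instruction to collect data before unblinding protects blinded assessment; it is not an AE cut-off. A reader might infer that removal harms go uncounted or that nobody may ask about them. The documents do not support that. What these duties lack is any scheduled contact that would find a new event.

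Other tempting inferences also fail:

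- **Number of removals.** The 162 in Section 15.4 is the Treatment number in the efficacy power calculation. It is not a count of removals: Section 7.5 requires removal before a withdrawing subject exits, and Section 7.6 calls removal imperative for all.
- **Procedure times.** The 12.9 and 10.9 minutes in Section 3.4.3 cover differently defined intervals and say nothing about comparative risk.
- **The precision figures.** The 80% and 2.0% are not errors. They weaken only under an assumed capture rate.
- **Timing of harms.** Section 3.5.2 gives no onset times, so how many removal harms would appear after discharge is unknown.

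Redaction also counts. Part of Section 11.9.10.1 and Sections 5.4, 5.5, 15.5.6 and 15.5.7 are hidden, and Appendix B has a Treatment-only footnote with no visible referent. A hidden post-removal contact cannot be excluded, although the visible exit text makes one unlikely.

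Finally, safety is descriptive (Section 6.3), and neither co-primary endpoint nor the blinding is affected. That limits the severity.

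**Conclusion.** The point holds as a gap in scheduled ascertainment. In the visible text, TPS removal is the only scheduled device procedure with no scheduled AE assessment after it, and the same is true of early removals. New harms after discharge reach the safety tables only by spontaneous report, so the removal safety profile may be under-counted.

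Up to 180 Treatment subjects are affected. The size of any under-count cannot be derived from the documents. Under assumed capture of 50% or 25% of delayed events, the chance of seeing a 0.9% event falls from 80.4% to 55.6% or 33.3%. The conclusion assumes that no redacted passage schedules a later contact. This is a cheap improvement that should be made; it does not threaten the efficacy conclusion.

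A related inconsistency needs reconciling. Section 11.9.10.1 has a 12-month endoscopic assessment in all subjects, while Sections 5.1 and 11.9.10 have none in Control. The answer affects when unblinding falls relative to the procedure.

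**What to change.** 1. In Section 11.9.10.1 and Appendix B, add an AE assessment after removal and before discharge.
2. Add one scripted AE telephone call to Treatment subjects after removal, for example in the 7 ± 2 day window already used after placement. The existing monthly calls in Section 11.9.12 carry no AE item, so this call needs its own script.
3. Apply both to early removals (Sections 7.5 and 10.5).
4. Define study exit for safety purposes as completion of that call.
5. In Section 15.5.5, state that AEs through the call are included and that removal-phase AEs are tabulated separately. Only Treatment subjects are called, so the separate table keeps the comparison with Control on like periods.
6. Reconcile Section 11.9.10.1 with Sections 5.1 and 11.9.10 on the 12-month endoscopy in Control.

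The cost is wording in the protocol, schedule and eCRF, one short call per Treatment subject by existing site staff, about a week's later safety exit, and possibly a higher Treatment AE count. The 12-month efficacy data, the order of unblinding and the clinical rules do not change. If a redacted passage already provides such a contact, a cross-reference in Section 11.9.10.1 and Appendix B would do for item 2.

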11.9.10.1. TPS Device Removal

The TPS is to be removed 365 ± 30 days after the index procedure under general or MAC anesthesia. An endoscopic assessment will be performed in all subjects followed by TPS removal in the Treatment group. The device removal procedure is described in detail in the IFU 

Subjects will be discharged according to the hospital and physician's discharge criteria.

All procedure- and device-related AEs must be followed until resolution or stabilization (the Investigator does not expect any further improvement or worsening of the event). Following study exit, follow-up will be according to clinical practice.

Subjects will be informed that his/her participation in this study is complete. The subject's study exit will be documented.

11.9.11. Unscheduled Visit

If a subject is hospitalized, seen in the emergency room, or has an unscheduled clinic visit, efforts should be made to collect the following data:

- Relevant medical history, physical examination, and laboratory testing findings
- Concomitant medications
- Assessment of AEs

These assessments should be documented on the eCRFs as appropriate.

11.9.12. Telephone Contact at Months 7 (210±7 days), 8 (240±7 days), 10 (300±7 days), and 11 (330-14 days)

In Months 7, 8, 10, and 11, subjects will be contacted by telephone by study personnel(s) who deliver(s) the lifestyle interventions. The subject and study personnel will have a brief (15-minute) telephone calls. During these calls, subjects will report on changes in weight, dietary intake, eating behavior, and physical activity level. These telephone calls are designed to promote adherence to the lifestyle modification protocol. The provider will reinforce positive behaviors consistent with the lifestyle modification program and problem solve issues related to weight gain, increased caloric intake or decreases in physical activity.

12. ASSESSMENT OF SAFETY

Safety will be evaluated through a risk-benefit assessment of the adverse events profile compared to the efficacy demonstrated by the TPS treatment. The incidence of Adverse Events (AEs), Serious AEs (SAEs), Serious Adverse Device Effects (SADEs), and Unanticipated Serious Adverse Device Effects (UADEs) will be captured.

12.1. Adverse Events

An AE is any untoward medical occurrence in a subject or clinical investigation subject that occurs during any part of the clinical study, whether related to the investigational device or not. Pre-existing conditions are not reported as AEs unless there has been a worsening in severity or frequency which cannot be attributed to the disease's natural history or progression. Protocol-defined follow-up visits and pre-scheduled endoscopies (including device placement/removal, patient surveillance, and planned diagnostic endoscopies) are not considered adverse events.

For AEs, the event description, severity, date of onset, treatment, outcome, and relationship to device will be collected on the AE eCRF.

All procedure- and device-related AEs must be followed until resolution or stabilization (the Investigator does not expect any further improvement or worsening of the event).

An Adverse Device Effect (ADE) is any adverse event that is considered possibly-related or related to the device. An ADE may occur at any time after exposure to the investigational device.

Determination of whether there is a reasonable possibility that the investigational device caused or contributed to an AE will be reported by the Investigator and reviewed by the CEC as described in Section 12.2.

Determination will be based on assessment of temporal relationships, biologic plausibility, association (or lack of association) with underlying disease, and presence (or absence) of more-likely cause.

12.1.1. Serious Adverse Event

A SAE is an event that:

- Led to a death
- Led to a serious deterioration in health resulting in
 - a life threatening illness or injury
 - a permanent impairment of a body structure or body function
 - in-patient hospitalization (>24 hours) or prolongation of an existing hospitalization
 - requires medical or surgical intervention to prevent life-threatening illness or injury or permanent impairment of a body structure or body function
- Led to fetal distress, fetal death or a congenital abnormality or birth defect

Here, “life-threatening” refers to an event when the patient is at substantial risk of dying at the time of the adverse event, it does not refer to an event that hypothetically might have caused death if it were more severe; “permanent” is defined as irreversible impairment or damage to a body structure or function, excluding trivial impairment or damage.

For the purpose of this study, endoscopic observations managed by medication and endoscopic surveillance as described in Guidelines for Managing Endoscopic Observations (Section 10.2.2) are not considered as SAEs. Diagnostic endoscopy is not considered as “intervention” in the context of SAE. Planned hospitalization for a pre-existing condition is not considered as a SAE.

12.1.2. Serious Adverse Device Effect

An SADE is a SAE that is possibly related or related to the device.

12.1.3. Unanticipated Adverse Device Effects

Unanticipated adverse device effects (UADE) are any serious adverse device effects on health or safety or any life-threatening problem or death caused by, or associated with, the investigational study device if that effect, problem, or death was not previously identified in nature, severity or degree of incidence in the investigational plan or application (including IFU) or any other unanticipated serious problem associated with a device that relates to the rights, safety, or welfare of subjects.

When an AE meets the definition of a UADE or that relationship is unknown, the Investigator will report the event to BAROnova within 24 hours but no later than 10 working days after the Investigator first learns of the effect and reports to the reviewing IRB as required.

